#### **14.3.8.2 Vital signs**

The change in vital signs (blood pressure, heart rate, body temperature) from baseline to each visit will be summarised by visit and treatment group as mean, standard deviation, median, minimum and maximum values for the safety analysis set.

#### **14.3.8.3 Clinical laboratory evaluation**

The change in each of the laboratory parameters from baseline to each visit will be summarised by visit and treatment group as mean, standard deviation, median, minimum and maximum values for the safety analysis set.

Laboratory parameters will be classified as 'low', 'normal' or 'high', depending on whether the value is below, within or above the reference range, respectively. A shift table will be produced showing the categories at baseline against those at end of treatment. Subjects with laboratory parameters outside the reference range will be listed.

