**Panel 2: Schedule of trial procedures (continued)**

Visit	Screening		Treatment period									Follow-up 			Uns. visit  (if appl.)	Early term.  (if appl.)	Nominal Week 16 visit  (if appl.)	References (protocol section)
	1 	2	3	4	5	6	7	8	9	10	11 	12 	13 	14 			11x	
Week	-6	-2	0	2	4	6	8	10	12	14	16	20	24	30			16	
Visit window (days) 	±3	-3	NA	±3	±3	±3	±3	±3	±3	±3	±3	±3	±3	±3	NA	NA	±3	
Investigator assessments of safety																		
Vital signs	X		X 	X 	X 	X	X	X	X	X	X			X	X 	X		11.4.1
Physical examination	X		X				X				X			X	X 	X		11.4.2
ECG	X		X								X			X	X 	X		11.4.3
Chemistry, haematology, IgE (central laboratory)	X 		X		X		X		X		X			X	X 	X		11.4.5
Serum pregnancy test; hepatitis B, C; HIV (central laboratory)	X																	11.4.4; 11.4.5
Urine pregnancy test			X		X		X		X		X			X	X 	X		11.4.4
Urinalysis	X		X		X		X		X		X			X	X 	X		11.4.5
Anti-drug antibodies			X		X						X			X	X 	X		11.4.6
Pharmacokinetics					X						X			X	X 	X		11.6
Adverse events	X	X	X	X	X	X	X	X	X	X	X	X	X	X	X 	X	X	13
Assessment of vaccine antibody response																		
Anti-tetanus response									X		X				X 	X 	X 	11.5
Anti-meningococcal response									X		X				X 	X 	X 	11.5

- 1) For subjects who do not require a wash-out, visits 1 and 2 will be combined and screening will be reduced to 2 weeks; hence, these subjects will only attend visit 2 (Week -2) which will include all assessments shown under Week -6. Similarly, for subjects who only require a 2-week wash-out, screening visits 1 and 2 will be combined (Week -2). The screening period has a maximum duration of 6 weeks.
- 2) Eligible subjects may roll over to the ECZTEND trial at Week 16 or later. See also footnote no. 5.
- 3) All subjects, except for those who roll over to the ECZTEND trial (LP0162-1337), will have a full 14-week off-treatment safety follow-up period. The safety follow-up period includes 2 telephone contacts and an office visit (end-of-trial visit) at Week 30. Subjects may transfer to the ECZTEND trial at any time during the safety follow-up period.
- 4) Visit will be conducted as a telephone contact.

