**Panel 6: Prohibited medication**

Medication	Prohibited from	Prohibited to	Temporary discontinuation of IMP required
Topical medications used for treatment of AD, including: 
 
• TCS of any WHO class.
 
• TCI.
 
• PDE-4 inhibitors.
 
	Week -2 (2 weeks prior to randomisation)	Week 16 (end of treatment)	No
Use of UVA or UVB, psoralen + UVA (PUVA), other phototherapy, or tanning beds.	Week -6 (6 weeks prior to randomisation)	Week 16 (end of treatment)	No
Three or more bleach baths per week.	Week -4 (4 weeks prior to randomisation)	Week 16 (end of treatment)	No
Investigational agents other than tralokinumab.	3 months or 5 half-lives  prior to randomisation	Week 30 (safety follow-up)	Yes
Immunoglobulin.	3 months or 5 half-lives  prior to randomisation	Week 30 (safety follow-up)	Yes
Blood products.	4 weeks prior to screening	Week 30 (safety follow-up)	Yes
Systemic corticosteroids 	Week -4 (4 weeks prior to randomisation)	Week 30 (safety follow-up)	Yes
Systemic treatment for AD with an immunosuppressive or immunomodulating agent  .	Week -4 (4 weeks prior to randomisation)	Week 30 (safety follow-up)	Yes
Allergen immunotherapy.	Randomisation	Week 30 (safety follow-up)	Yes
Vaccination of any kind (except influenza virus vaccines).	3 months prior to screening	Week 30 (safety follow-up)	Yes

1) Whichever is longer. For cell-depleting agents, the use is disallowed within 6 months of randomisation.

2) Note: nasal and inhaled corticosteroids are allowed.

3) Examples include cyclosporine, mycophenolate mofetil, azathioprine, methotrexate, Janus kinase inhibitors, interferon-gamma, dupilumab, and other biologics.

AD, atopic dermatitis; IMP, investigational medicinal product; PDE-4, phosphodiesterase 4; TCI, topical calcineurin inhibitor; TCS, topical corticosteroid; UV, ultraviolet; WHO, World Health Organization.

In case any prohibited treatments are used during the trial, they must be recorded as concomitant medication.

Refer to Section 9.5 for principles for use of rescue treatment and re-initiation of IMP after discontinuation of prohibited systemic rescue treatment.

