### 10.2 IMP discontinuation rules

#### 10.2.1 Reasons for permanent discontinuation of IMP

Subjects will be permanently discontinued from IMP in the event of:

- Anaphylactic reaction or other severe systemic reaction to IMP injection.
- An AE that, in the opinion of the investigator or sponsor's medical expert, contraindicates further dosing.
- Diagnosis of a malignancy during the trial, excluding carcinoma in situ of the cervix, or localised squamous or basal cell carcinoma of the skin.
- Evidence of pregnancy.
- Any infection that is opportunistic, such as active tuberculosis and other infections whose nature or course may suggest an immuno-compromised status.
- Severe laboratory abnormalities:
  - ALT and/or AST values >3x ULN with total bilirubin >2x ULN (unless elevated bilirubin is related to Gilbert-Meulengracht Syndrome).
  - Confirmed AST and/or ALT >5x ULN (for more than 2 weeks).

Refer to Section [10.3](#) for details on the handling of subject discontinuation and to [Panel 2](#) for assessments to be performed at an early termination visit for subjects who discontinue IMP permanently.

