### End-of-treatment form

An end-of-treatment form will be completed when the subject has had their last administration of IMP. The following data will be recorded on this form:

- Date of last administration of IMP (tralokinumab/placebo).
- Has the subject completed the treatment period (yes/no). If no, the primary reason for permanent discontinuation of IMP must be recorded (lack of efficacy, AE, withdrawal by subject, lost to follow-up, death, other).

The primary reason for permanent discontinuation of IMP must also be recorded in the medical records.

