6.9.2 Definition of trial periods and date of permanent discontinuation of IMP

Date of permanent discontinuation of IMP (tralokinumab/placebo)

Defined for subjects who have a reason for permanent discontinuation of IMP (tralokinumab/placebo) recorded.

Defined as the latest of date of early termination visit (if existing) or date of onset of latest AE leading to withdrawal of trial product, otherwise date of the last visit, excluding safety follow-up and nominal Week 16 visits.

Exposure start

Date and time of first dose.

Exposure end

Date of Week 16 visit (if existing) at time 23:59:00, otherwise date of permanent discontinuation of IMP (tralokinumab/placebo) at time 23:59:00.

Trial periods

The time from exposure start to exposure end will be assigned to the treatment period and remaining time after exposure end will be assigned to the safety follow-up period as shown in [Table 6](#) (ADaM variable APHASE). The ADaM variable APERIODC will indicate the latest treatment at any given time point, thus not including a follow-up period ([Table 7](#)).

Table 6: Start and end time of trial periods (ADaM variable APHASE)

APHASE	Start of period	End of period (only if start date exists)
Treatment period	Exposure start	Exposure end
Safety follow-up period ¹	Exposure end (plus 1 second)	Date of safety follow-up visit (if existing) at time 23:59:00 else Date of last contact at time 23:59:00

1) Only applicable if date of last contact is not equal to date of exposure end.

Table 7: Start and end time of trial periods (ADaM variable APERIODC)

APERIODC	Start of period	End of period (only if start date exists)
-----------------	------------------------	--

Treatment period	Exposure start	Date of last contact at time 23:59:00
------------------	----------------	---------------------------------------

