6.9.4 Early termination and unscheduled visits

When no data are available from a certain scheduled post-baseline visit for a particular subject, data from early termination visits and unscheduled visits have the potential to replace data from that particular scheduled visit in data summaries, provided the data are collected between 6 days before and 7 days after the planned time point for the scheduled visit, as displayed below.

Visit (target day)	Visit window (day is date of assessment minus date of first dose)
Week 2 (Day 14)	Day 8 to 21
Week x (Day 7*x) (where x= 4, 6, ..., 16)	Day 7*x-6 to 7*x+7
Safety follow-up	106-119 days after last dose

When both unscheduled and early termination visits exist within the given visit window, the early termination visit will be selected for analysis. When no early termination visit and several unscheduled visits exist, the unscheduled visit closest to the target day will be selected for analysis. If the difference is a tie, the latest unscheduled visit will be selected.

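### The only laboratory shift table compares baseline with an undefined end of treatment, so out-of-range values at Weeks 4, 8 or 12 that resolve by then are not counted by arm in it

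*Protocol*

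**What the plan says.** Protocol 14.3.8.3 classifies each laboratory value as low, normal or high against the reference range and plans one cross-tabulation: "A shift table will be produced showing the categories at baseline against those at end of treatment". The same section adds two other outputs. One is "The change in each of the laboratory parameters from baseline to each visit will be summarised by visit and treatment group", using mean, standard deviation, median, minimum and maximum. The other is a listing of subjects with out-of-range values, which is not restricted to any visit.

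In Panel 2 the row "Chemistry, haematology, IgE (central laboratory" is marked at screening, Weeks 0, 4, 8, 12, 16 and 30, at early termination, and at unscheduled visits at the investigator's discretion. It is empty in the column for the nominal Week 16 visit (11x), which subjects who stop early are asked to attend.

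SAP 6.8.4 defines limits for potentially clinically significant values in Table 4 and says that the latest of several values at one visit is used. It does not alter the shift table, and it does not say whether Table 4 exceedances are counted at any time, by visit or at the last value.

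Neither document defines end of treatment for this table. Panel 6 writes "Week 16 (end of treatment" for the end date of some prohibited medications. Protocol 11.10 says "An end-of-treatment form will be completed when the subject has had their last administration of IMP". SAP 6.9.2 sets exposure end as "Date of Week 16 visit (if existing) at time 23:59:00, otherwise date of permanent discontinuation of IMP (tralokinumab/placebo) at time 23:59:00".

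**The concern.** A shift table is where a reader looks to compare, arm against arm, how many subjects moved out of the reference range. If it looks at a single time point, a subject who was high at Week 4 and Week 8 and normal at Week 16 is counted as never having shifted. A treatment effect that is transient or early could then leave no trace in the one planned by-arm count of low, normal and high status.

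The undefined end point adds a second problem. Protocol 10.2.1 includes laboratory reasons for permanent discontinuation, for example "Confirmed AST and/or ALT >5x ULN (for more than 2 weeks". Whether such subjects appear in the table depends on which meaning of end of treatment the programmer adopts, and the two meanings give different denominators.

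**Working it through.** The plan states no figure on this point, so there is nothing to reproduce. The check consists of counts and a comparison of sections.

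**1. Samples used.** On-treatment samples after baseline (Panel 2): Weeks 4, 8, 12 and 16, so 4. For a completer the table uses 1 of them, and 4 − 1 = 3 are not used. This is a count of visits, not a probability. An abnormality that persists to the end is fully captured; one that resolves is not captured at all.

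**2. One subject followed through.** Take gamma glutamyl transferase that is normal at baseline, high at Weeks 4 and 8, and normal at Weeks 12 and 16.

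| Output | What it shows |
|---|---|
| Shift table (14.3.8.3) | normal to normal |
| By-visit change (14.3.8.3) | visible only if this subject sets that visit's maximum; no count of subjects |
| Out-of-range listing (14.3.8.3) | shown; no count or percentage by arm |
| AE tables (11.4.5, 14.3.8.1) | counted by arm only if the investigator judged it clinically significant |
| SAP Table 4 | no limit for this parameter |

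**3. Parameters without a Table 4 limit.**
- Panel 11: 18 chemistry (tryptase left out, as it is measured only in suspected anaphylaxis) + 17 haematology + IgE = 36.
- SAP Table 4: 13 biochemistry + 7 haematology = 20.
- Without a limit: 36 − 20 = 16. These are urea nitrogen, gamma glutamyl transferase, lactate dehydrogenase, albumin, protein, erythrocytes, haematocrit, mean corpuscular volume, mean corpuscular haemoglobin concentration, leukocytes, five leukocyte percentages, and IgE.
- The five percentages have absolute counts in Table 4, so 16 − 5 = 11 have no counterpart there.
- Four of those 11 are red-cell measures that stand beside haemoglobin, which has a limit: 11 − 4 = 7.

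**4. Early stoppers, under each meaning of end of treatment.**
- *Week 16 visit.* SAP 6.9.4 lets an early-termination or unscheduled value stand in for a missing scheduled one, "provided the data are collected between 6 days before and 7 days after the planned time point for the scheduled visit". For Week 16 that is Day 7×16 − 6 = 106 to Day 7×16 + 7 = 119. Visit 11x takes no chemistry or haematology sample. A subject who stops before Day 106, with no unscheduled sample in the window, therefore has no Week 16 laboratory value and leaves the table. A sample taken on Days 106 to 119 keeps the subject in.
- *Subject's own last on-treatment assessment.* Panel 2 takes the laboratory sample at early termination. SAP 6.9.2 dates permanent discontinuation no earlier than the early-termination visit, if there is one, so that sample lies within the treatment period. The subject is in the table, and an abnormality still present at that visit is shown.

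**5. Repeat tests.** Protocol 11.4.5 requires clinically significant abnormal tests at baseline or later to be repeated. If the repeat is recorded under the same visit, the latest-value rule in SAP 6.8.4 can replace the abnormal value in the by-visit summaries too. The documents do not say under which visit a repeat is recorded.

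**The case against.** **Transient values are covered elsewhere.** In the record they are: the listing holds every out-of-range subject, and clinically significant findings become AEs that are tabulated and compared by arm. What stands is that no data are lost. What does not follow is that the comparison is made: the listing has no counts, minimum and maximum show only the extreme subject, and the AE route covers only what the investigator judged clinically significant.

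**The count of 16 flatters the point.** This stands as a matter of weight. After the leukocyte percentages and red-cell measures are set aside, 7 parameters remain.

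**Lowest and highest category is a reporting preference and picks up noise.** It does pick up isolated excursions, in both arms. Laboratory shifts are also not among the endpoints in Panel 3. But safety is a stated objective there, and the added table uses data already collected.

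**A stronger reading that does not hold.** A reader might infer that subjects whose laboratory values made them stop vanish from the table. The documents do not say so. That reading needs end of treatment to mean the Week 16 visit, and the support for it is a parenthesis in the prohibited-medication panel. The end-of-treatment form and SAP exposure end point at least as well to a subject-level meaning, which keeps the early-termination sample. Even on the Week 16 meaning, Days 106 to 119 are retained. The liver example is also weaker than it looks, because ALT, AST and bilirubin have Table 4 limits that include the multiples used in 10.2.1.

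**Conclusion.** The point holds in a limited form. Under either meaning of end of treatment, a value out of range at Week 4, 8 or 12 that has normalised by then is not counted by arm in the only laboratory shift table. For 16 of 36 scheduled parameters (11 once the leukocyte percentages are set aside) no other categorical summary is specified. Separately, end of treatment is undefined for this table, and the two available meanings treat subjects who stop before Day 106 in opposite ways.

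The size cannot be put more precisely from the documents. How many abnormalities are missed depends on how long they last and when they occur, and neither is given. It should not be expressed as a loss of power either, since no hypothesis test is planned on the shift table. No primary or secondary efficacy conclusion is affected; what suffers is the ability to see a transient laboratory signal by arm. The parameter count assumes that each Panel 11 parameter, IgE included, has a reference range and enters the shift table.

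**What to change.** In Protocol 14.3.8.3 and SAP 6.8.4:

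- Produce, by arm, shifts from the baseline category to the lowest and to the highest category over all post-baseline samples in the treatment period, including early-termination and unscheduled samples. SAP 6.9.2 already supplies the period limits.
- State that the latest-value-per-visit rule does not apply to these two tables; otherwise a normal repeat could erase the value they are meant to show.
- If an end-of-treatment column is kept, define it as the last sample in the treatment period, so that early stoppers are included.
- State that Table 4 exceedances are counted at any time post-baseline in the treatment period.

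The cost is wording and a small programming change, with no new samples or visits. The downside is that more isolated out-of-range values will appear in both arms, so the tables should be read as a comparison between arms rather than by their absolute counts.

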#### **14.3.8.4 Pharmacokinetics**

All the PK samples in the trial are trough samples. The  $C_{\text{trough}}$  concentration will be listed by treatment group and descriptive statistics will be provided.

$C_{\text{trough}}$  values from subjects with positive ADA/nAb will be compared to values from subject with negative ADA/nAb if data permits.

The PK data will be merged with those from other clinical trials with tralokinumab for a population-based meta-analysis. Results of the meta-analysis will be presented in a separate pharmacometrics report outside of the CTR.

### 14.3.8.5 Anti-drug antibodies

ADA status (positive versus negative) at each visit will be summarised by treatment group. If considered relevant, descriptive statistics including number of subjects, mean, standard deviation, median, and range of the actual ADA titres by treatment group and visit will be provided. The ADA status across the trial for each subject (positive versus negative) will also be classified and summarised by treatment group.

The association of ADA status across the trial (positive versus negative) with AEs/SAEs may be evaluated. In addition, the association of ADA titres ( $\geq$  median titre in positive subjects versus  $<$  median titre) with AE/SAEs may be evaluated for ADA-positive treated subjects only. The ADA-positive subjects across the trial may also be divided into persistent positive versus transient positive. A subject will be considered as persistent positive if he/she has positive ADA for at least 2 consecutive visits with ADA assessment. Otherwise, the subject will be considered as transient ADA positive. The associations between ADA and AE/SAEs may be summarised for both persistent positive subjects versus transient positives subjects.

For subjects who develop ADA, the IGA score and change in EASI at end of treatment will be listed.

Evaluations of nAB will be conducted on those serum samples that test positive for ADA. The test sample is deemed positive or negative for the presence of nAb to tralokinumab relative to a pre-determined (in assay validation), statistically derived cut point.

For ADA, all subjects with titre information will be listed.

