### **Safety follow-up period (Week 16 to Week 30)**

All subjects, except for those who transfer to the ECZTEND trial (LP0162-1337), will complete a full 14-week off-treatment follow-up period which includes 2 telephone contacts and an office visit at Week 30 for assessment of safety, PK, and ADA.

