### **Long-term extension trial**

Eligible subjects may be invited to enter an open-label, long-term extension trial conducted under a separate protocol (LP0162-1337, ECZTEND). Subjects who fulfil the eligibility criteria in the ECZTEND protocol can enter the trial at the Week 16 visit or up to 16 weeks after the last IMP injection in the present trial. Subjects who transfer to ECZTEND must have had their Week 16 visit under the current protocol (LP0162-1341).

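### Protocol 14.3.8.5 labels an isolated positive in the last available ADA sample as transient, although its persistence is undetermined

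*Protocol*

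**What the plan says.** Protocol 14.3.8.5 makes the split optional: "The ADA-positive subjects across the trial may also be divided into persistent positive versus transient positive". The rule for the first class is: "A subject will be considered as persistent positive if he/she has positive ADA for at least 2 consecutive visits with ADA assessment". Everyone else who is ADA-positive falls into the second class: "Otherwise, the subject will be considered as transient ADA positive". The stated use of the split is also optional: "The associations between ADA and AE/SAEs may be summarised for both persistent positive subjects versus transient positives subjects".

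The row "Anti-drug antibodies" in Panel 2 places scheduled samples at Weeks 0, 4, 16 and 30, with further samples at an early termination visit and, at the investigator's discretion, at unscheduled visits. Weeks 20 and 24 are telephone contacts. Section 7.1 confirms that subjects who do not transfer have an "office visit at Week 30 for assessment of safety, PK, and ADA". Subjects eligible for the extension trial "can enter the trial at the Week 16 visit or up to 16 weeks after the last IMP injection in the present trial".

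SAP 6.8.6 sorts ADA status into pre-existing, treatment-boosted, treatment-emergent, negative, and no post-baseline assessment. It neither uses nor alters the persistent/transient rule.

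**The concern.** In ordinary reading, transient says that a response came and went. The rule gives that label to any subject without two adjacent positives, including a subject who was positive when last tested and never tested again. If the split is tabulated, its transient row would combine two kinds of subject: those with a later negative result, and those whose positive result was never followed up. An AE/SAE comparison between the two rows would then be hard to interpret, because part of the transient row has unknown persistence.

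The sampling schedule makes this a practical possibility. The gap from Week 4 to Week 16 covers 12 of the 16 treatment weeks, and for a subject who transfers before Week 30, Week 16 is normally the last ADA result in this trial.

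**Working it through.** The documents give no figure on this point, so there is none to reproduce. The check applies the rule of 14.3.8.5 to every possible sequence of results.

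**Inputs.** Scheduled samples are at Weeks 0, 4, 16 and 30 (Panel 2). With full follow-up there are k = 4 samples; with transfer before Week 30 and no extra sample there are k = 3 (Weeks 0, 4, 16). Persistent requires two adjacent positives; transient is any other sequence with at least one positive.

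**Formulas.** There are 2^k sequences, of which 2^k − 1 contain a positive. Let a(k) be the number of sequences with no two adjacent positives: a(1) = 2, a(2) = 3, a(k) = a(k−1) + a(k−2), so a(3) = 5 and a(4) = 8. Removing the all-negative sequence gives a(k) − 1 transient sequences. A transient sequence that ends on a positive must have a negative just before it, so there are a(k−2) of these.

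| | Full follow-up (k = 4) | Last sample at Week 16 (k = 3) |
|---|---|---|
| Any positive | 16 − 1 = 15 | 8 − 1 = 7 |
| Transient | 8 − 1 = 7 | 5 − 1 = 4 |
| Persistent | 15 − 7 = 8 | 7 − 4 = 3 |
| Transient, last sample positive | a(2) = 3 | a(1) = 2 |

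The transient sequences that end on a positive are:

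- full follow-up: − − − +, − + − +, + − − +
- last sample at Week 16: − − +, + − +

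A subject first positive at the last sample (− − − + or − − +) is always labelled transient. When Week 16 is the last sample, a baseline-negative subject can be persistent only by being positive at both Week 4 and Week 16.

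**Baseline-negative subjects only.** With full follow-up there are 4 transient sequences (− − − +, − − + −, − + − −, − + − +), of which 2 end positive. With Week 16 as the last sample there are 2 (− − +, − + −), of which 1 ends positive. The finding therefore does not depend on counting subjects who were already positive at baseline.

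**After the change proposed below.** Transient falls from 7 to 7 − 3 = 4 sequences with full follow-up, and from 4 to 4 − 2 = 2 with Week 16 as the last sample. The 3 and 2 sequences removed become indeterminate.

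These counts show which result patterns the rule covers. They say nothing about how often each pattern would occur.

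**The case against.** The strongest reply is that the protocol defines transient operationally, as positive without two consecutive positives, and that a label cannot be wrong under its own definition. This stands in part. A reader might infer that these subjects are misclassified, but the documents do not support that: their true status is unknown and some may indeed be transient. The supportable statement is that an undetermined status receives a label suggesting resolution.

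The second reply is that little depends on the split. This stands. A reader might take the persistent-versus-transient comparison as a committed analysis, but both the division and the AE/SAE summary are worded as things that may be done, and neither belongs to the testing hierarchy. The secondary endpoint is the presence of ADA, which the split does not touch. A baseline-negative subject first positive at the last sample is properly treatment-emergent under SAP 6.8.6. Subjects with titre information are also listed.

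Two further inferences go beyond the documents:

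- **That the labelling depends on how subjects fared, because transfer does.** Section 7.1 ties transfer to eligibility criteria in the extension protocol, which is not among the documents. Section 12 says that subjects who do not achieve or who lose response are not excluded from further participation.
- **That every transferring subject who converts after Week 4 must be called transient.** Transfer is possible up to 16 weeks after the last injection at Week 14, that is, up to Week 30. The end-of-trial form in section 11.10 lists Week 30 as a possible last visit before transfer, so some of these subjects can have a Week 30 sample. An unscheduled sample could also supply a second consecutive positive.

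**Conclusion.** The point holds as a labelling defect of small consequence. The rule in 14.3.8.5 calls a subject transient when the last available sample is an isolated positive, and nothing elsewhere in the protocol or SAP corrects this. On scheduled samples it covers 3 of 7 transient patterns with full follow-up and 2 of 4 when Week 16 is the last sample. The second figure assumes transfer before Week 30 and no early termination or unscheduled ADA sample.

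The documents give neither an ADA incidence nor a transfer rate, so the number of subjects affected cannot be computed. The consequence is limited to the optional, descriptive AE/SAE summary by persistence. No primary or secondary endpoint and no committed ADA output changes.

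**What to change.** If the split is produced, keep the definition of persistent ("positive ADA for at least 2 consecutive visits with ADA assessment") and divide the remaining ADA-positive subjects by their last available ADA sample:

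- **Transient:** not persistent, last available ADA sample negative.
- **Indeterminate:** not persistent, last available ADA sample positive; shown as a separate row.

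The rule should refer to the last available sample rather than to subjects whose only positive is the last one. That narrower rule would leave − + − +, + − − + and + − + in the transient class although they also end on a positive; transient would fall only from 7 to 6 patterns, or from 4 to 3.

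The change takes about one sentence, most naturally in SAP 6.8.6, and one table row. Section 14.3.10 already allows changes to the planned analysis through a protocol amendment, the SAP update or the clinical trial report. No new sampling is needed. The cost is a smaller transient group and one more category in a table that may already be sparse.
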